7.6.5.1 Additional laboratory assessments

For any safety event or laboratory abnormality, additional laboratory assessments, imaging, and consultation may be performed for clinical evaluation and/or in consultation with the study Medical Monitor; results may be collected and should be included in the clinical database.

Additional laboratory assessments will be performed in patients who experience any LFT abnormalities during either the factor or BPA prophylaxis period (BPA prophylaxis period is not applicable for the subgroup of Cohort A patients who are not responding adequately to BPA prophylaxis treatment) or the fitusiran treatment period. Following the occurrence of elevated liver transaminases or other LFT abnormalities per the central laboratory, all assessments in [Table 8](#) will be performed one time, as well as hematology, serum chemistry, LFT, and coagulation assessments from [Table 7](#), AT levels, and other assessments or evaluations per Investigator discretion, as appropriate. For the United States specific requirements, see [Section 11.6.1.2](#).

For patients in the fitusiran treatment period, monitoring and dose modification will also be performed as outlined in [Section 6.2.3.1](#).

Table 8 - Hepatic assessments in patients who experience LFT elevations

| Extended Hepatic Panel | |
|--|---|
| Herpes Simplex Virus 1 and 2 antibody IgM, IgG | Herpes Zoster Virus IgM, IgG |
| HIV 1 and 2 ^a | HHV-6 |
| Cytomegalovirus antibodies, IgM, IgG | HBs Ag, HBc antibody IgM and IgG |
| Anti-nuclear antibodies | Epstein-Barr Virus antibodies, IgM and IgG |
| Anti-smooth muscle antibodies | Anti-mitochondrial antibodies |
| HCV antibody | HAV antibody IgM |
| HCV RNA PCR – qualitative and quantitative | HEV antibody IgM |
| Imaging | |
| Abdominal ultrasound with Doppler flow (or CT or MRI) including right upper quadrant | |
| Focused Medical and Travel History | |
| Use of any potentially hepatotoxic concomitant medications, including over the counter medications and herbal remedies | Alcohol consumption |
| Other potentially hepatotoxic agents including any work-related exposures | Recent travels to areas where hepatitis A or E is endemic |

Note: All assessments will be measured in central laboratory. The full panel of assessments should only be performed once; individual assessments may be repeated, as needed

Abbreviations: CT=computed tomography; HAV=hepatitis A virus; HBc=hepatitis B core; HBsAg=hepatitis B virus surface antigen; HCV=hepatitis C virus; HEV=hepatitis E virus; HHV-6=human herpesvirus 6; HIV=human immunodeficiency virus; IgG=immunoglobulin G antibody; IgM=immunoglobulin M antibody; MRI=magnetic resonance imagery; PCR=polymerase chain reaction; PT=prothrombin time; RNA=ribonucleic acid

^a HIV testing will not be performed where prohibited by local regulations.

7.6.5.2 Immunogenicity

Blood samples will be collected to evaluate antidrug antibodies (ADAs) to fitusiran. Blood samples for ADA testing must be collected within 4 hours before study drug administration as specified in the Schedule of Assessments (Table 1). In addition, a blood sample to evaluate ADAs will be collected at the ET visit, if applicable.

Details regarding the processing, shipping, and analysis of the samples are provided in the Laboratory Manual.

7.6.6 Adverse events

7.6.6.1 Definitions

Adverse Event

According to the International Conference on Harmonisation (ICH) E2A guideline Definitions and Standards for Expedited Reporting, and 21 Code of Federal Regulations (CFR) 312.32, IND

Safety Reporting, an adverse event (AE) is any untoward medical occurrence in a patient or clinical investigational subject administered a medicinal product and which does not necessarily have a causal relationship with this treatment. Since bleeding episodes are recorded as an efficacy assessment of fitusiran, these will not be treated as AEs unless they meet any of the SAE criteria listed in [Section 7.6.6.1](#).

Serious Adverse Event

An SAE is any untoward medical occurrence that at any dose:

- Results in death
- Is life-threatening (an event which places the patient at immediate risk of death from the event as it occurred. It does not include an event that had it occurred in a more severe form might have caused death)
- Requires in-patient hospitalization or prolongation of existing hospitalization
- Results in persistent or significant disability or incapacity
- Is a congenital anomaly or birth defect
- Is an important medical event that may not be immediately life-threatening or result in death or hospitalization but may jeopardize the patient and may require intervention to prevent one of the other outcomes listed in the definition above (eg, events include allergic bronchospasm requiring intensive treatment in an emergency room or at home, blood dyscrasias, convulsions, or the development of drug dependency or abuse).
- Bleeding episodes will be recorded as an efficacy assessment of fitusiran and will not be treated as AEs unless they meet any of the above criteria for SAEs.

Adverse Events of Special Interest

The following events are considered to be AEs of special interest (AESI):

- ALT or AST elevations $>3 \times$ ULN
- Suspected or confirmed thrombosis
- Severe or serious ISRs, ISRs that are associated with a recall phenomenon (reaction at the site of a prior injection with subsequent injections), or those that lead to temporary dose interruption or permanent discontinuation of fitusiran
- Systemic injection associated reactions (IARs), defined as hypersensitivity reactions which are related or possibly related to IMP.
- Cholecystitis
- Cholelithiasis

Adverse Event Severity

Adverse events are to be graded according to the categories detailed below:

| | |
|-----------|---|
| Mild: | Mild; asymptomatic or mild symptoms; clinical or diagnostic observations only; intervention not indicated |
| Moderate: | Moderate; minimal, local or noninvasive intervention indicated; limiting age appropriate instrumental activities of daily living (eg, preparing meals, shopping for groceries or clothes, using the telephone, managing money) |
| Severe: | Severe or medically significant but not immediately life-threatening; hospitalization or prolongation of hospitalization indicated; disabling; limiting self-care activities of daily living (ie, bathing, dressing and undressing, feeding self, using the toilet, taking medications, and not bedridden); OR life-threatening consequences; urgent intervention indicated; OR death related to an adverse event |

Changes in severity should be documented in the medical record to allow assessment of the duration of the event at each level of severity. Adverse events characterized as intermittent require documentation of the start and stop of each incidence. When changes in the severity of an AE occur more frequently than once a day, the maximum severity for the experience that day should be noted. If the severity category changes over a number of days, then those changes should be recorded separately (with distinct onset dates).

AE severity and seriousness are assessed independently. ‘Severity’ characterizes the intensity of an AE. ‘Serious’ is a regulatory definition and serves as a guide to the Sponsor for defining regulatory reporting obligations (see definition for SAE).

Relationship of the Adverse Event to Study Treatment

The relationship of each AE to study treatment should be evaluated by the Investigator using the following criteria:

| | |
|---------------------|---|
| Definitely related: | A clinical event, including laboratory test abnormality, occurring in a plausible time relationship to the medication administration, and which cannot be explained by concurrent disease or other drugs or chemicals. The response to withdrawal of the drug should be clinically plausible. |
| Possibly related: | A clinical event, including laboratory test abnormality, with a reasonable time sequence to the medication administration, but which could also be explained by concurrent disease or other drugs or chemicals. Information on the drug withdrawal may be lacking or unclear. |
| Unlikely related: | A clinical event, including laboratory test abnormality, with little or no temporal relationship to medication administration, and which other drugs, chemicals, or underlying disease provide plausible explanations. |
| Not related: | A clinical event, including laboratory test abnormality that has no temporal relationship to the medication or has more likely alternative etiology. |

7.6.6.2 Eliciting and recording adverse events

Eliciting Adverse Events

The patient should be asked about medically relevant changes in his health since the last visit, with attention to any signs and symptoms that could be consistent with thrombosis. The patient should also be asked if he has been hospitalized, had any accidents, used any new medications, or changed concomitant medication routines (both prescription and over the counter [OTC]). In addition to patient observations, AEs will be documented from any clinically relevant laboratory findings, physical examination findings, ECG changes, or other findings that are relevant to patient safety.

Recording Adverse Events

The Investigator is responsible for recording non-serious AEs and SAEs that are observed or reported by the patient after the time when the informed consent is signed regardless of their relationship to study drug through the end of study. Non-serious AEs will be followed until the end of study. SAEs will be followed until satisfactory resolution, until baseline level is reached, or until the SAE is considered by the Investigator to be chronic or the patient is stable, as appropriate.

All AEs must be recorded in the source records for the clinical study center and in the eCRF for the patient, whether or not they are considered to be drug related. Each AE must be described in detail: onset time and date, description of event, severity, relationship to investigational drug, action taken, and outcome (including time and date of resolution, if applicable).

For SAEs, record the event(s) on both the eCRF and the SAE form.

For AEs that are considered AESI ([Section 7.6.6.1](#)), the Sponsor or its designee should be notified within 24 hours using a supplemental AESI eCRF. Additional clinical and laboratory information may be collected; see [Section 6.2.3.1](#) regarding monitoring for liver abnormalities.

Refer to the eCRF completion guidelines for details on reporting events in the supplemental AESI eCRF.

Since bleeding episodes are recorded as an efficacy assessment of fitusiran, these will not be treated as AEs unless they meet any of the SAE criteria listed in [Section 7.6.6.1](#). The manifestation and frequency of bleeding episodes is an efficacy indicator of this study and ABR is the focus of the primary and secondary efficacy analyses.

Recording an ISR

For all ISRs, the Investigator, or delegate, should submit a supplemental ISR eCRF, recording additional information (eg, descriptions, onset and resolution date, severity, treatment given, event outcome). An ISR is defined as a local reaction at or near the site of injection. “At or near” the injection site includes reactions at the injection site, adjacent to the injection site, or a reaction which may shift slightly away from the injection site due to gravity (eg, as may occur

with swelling or hematoma). Reactions with onset and resolution within 4 hours of the injection (eg, transient pain/burning at injection site) do not meet the study definition of ISRs, unless immediate treatment is required. A systemic reaction which includes the injection site, eg, generalized urticaria, other distinct entities or conditions like lymphadenopathy that may be near the injection site is not considered an ISR.

7.6.6.3 *Serious adverse events and adverse events of special interest require immediate reporting to Sponsor/Designee*

An assessment of the seriousness of each AE will be made by the Investigator. Any AE and laboratory abnormality that meets the SAE criteria in [Section 7.6.6.1](#) and any AESI must be reported to the Sponsor or designee within 24 hours from the time that clinical study center staff first learns of the event. All SAEs must be reported regardless of the relationship to study drug.

The initial report should include at least the following information:

- Patient's study number
- Description and date of onset of the event
- Criterion for serious
- Preliminary assignment of relationship to study drug, and
- Investigator/site information

To report the SAE, complete the SAE form. Within 24 hours of receipt of follow-up information, the Investigator must update the SAE form.

Appropriate remedial measures should be taken by the Investigator using his/her best medical judgment to treat the SAE. These measures and the patient's response to these measures should be recorded. All SAEs, regardless of relationship to study drug, will be followed by the Investigator until satisfactory resolution or the Investigator deems the SAE to be chronic or stable. Clinical, laboratory, and diagnostic measures should be employed by the Investigator as needed to adequately determine the etiology of the event.

7.6.6.4 *Sponsor safety reporting to Regulatory Authorities*

The Sponsor or its representative will report certain study events in an expedited manner to the Food and Drug Administration, the European Medicines Agency's EudraVigilance electronic system according to Directive 2001/20/EC, and to all country Regulatory Authorities where the study is being conducted, according to local applicable regulations.

7.6.6.5 Serious adverse event notification to the Institutional Review Board/Independent Ethics Committee

Suspected unexpected serious adverse reactions (SUSARs) will be reported to the IRB/IEC per their institutional policy by the Investigator or Sponsor (or Sponsor designee) according to country requirements. Copies of each report and documentation of IRB/IEC notification and acknowledgement of receipt will be kept in the Investigator's study file.

7.6.6.6 Pregnancy reporting

There will only be male patients in this study.

The reporting of any pregnancy outcome for a female partner of a male patient participating in this study that results in a postpartum complication, spontaneous abortion, stillbirth, neonatal death, or congenital anomaly should be reported to the Investigator, who will then report this to the Sponsor or designee. The pregnancy outcome is to be recorded on the pregnancy reporting form.

7.6.6.7 Overdose reporting

An overdose is defined as any dose administered to or taken by a patient (accidentally or intentionally) that exceeds the highest daily dose, or is at a higher frequency, than included in the protocol. Overdose must be recorded in the eCRF.

All reports of overdose (with or without an AE) must be reported within 24 hours to the Sponsor or designee.

7.6.6.8 Guidelines for reporting product complaints/medical device incidents (including malfunctions)

Any defect in the IMP must be reported as soon as possible by the Investigator to the monitoring team that will complete a product complaint form within required timelines.

Appropriate information (eg, samples, labels or documents like pictures or photocopies) related to product identification and to the potential deficiencies may need to be gathered. The Investigator will assess whether or not the quality issue has to be reported together with an AE or SAE.

7.7 OTHER ASSESSMENTS

7.7.1 Patient-reported outcomes

Patient-reported outcomes will be utilized in this study where available to assess health-related quality of life (HRQOL), physical activity, and treatment satisfaction and health utility. The age of the patient at Enrollment will determine which age-specific versions of questionnaires will be utilized and will be in force for the study duration. All completed questionnaires or instrument forms for the patient-reported outcome assessments described below will be collected, entered into a database, and archived at study sites.

The Sponsor or designee will provide the translations for all survey instruments, where translations are available. The sites must not translate any survey instruments.

7.7.1.1 HRQOL instruments: Haem-A-QOL and Haemo-QOL

The Haemophilia Quality of Life Questionnaire for Adults (Haem-A-QOL) and Haemophilia Quality of Life Questionnaire for Children and Adolescents (Haemo-QOL) are psychometrically tested QOL assessment instruments for patients with hemophilia (19). The Haem-A-QOL will be provided to patients ≥ 17 years of age, and includes 46 items contributing to 10 QOL domains (physical health, feelings, view of yourself, sports and leisure, work and school, dealing with hemophilia, treatment, future, family planning, partnership and sexuality). Scoring for each item is based on a 5-point Likert scale (never, rarely, sometimes, often, and all the time), and higher scores represent greater impairment.

The Haemo-QOL (Children's short version for age groups II/III [8-16 years of age]) will be provided to patients < 17 years of age, to self-complete as specified in the Schedule of Assessments (Table 1). The same questionnaire used during the Month 7 visit will be utilized throughout the study.

7.7.1.2 TSQM-9

The Treatment Satisfaction Questionnaire for Medication (TSQM) will assess patient satisfaction with treatment. The TSQM is a validated psychometric tool that provides a general measure of patient satisfaction with medication (20). Where available, the TSQM questionnaire will be distributed to patients to self-complete as specified in the Schedule of Assessments (Table 1).

7.7.1.3 HAL

The Haemophilia Activities List (HAL) and Paediatric HAL (pedHAL) questionnaires will assess subjective functional ability to perform activities of daily living (21). The HAL will be assessed in patients ≥ 18 years of age, and the pedHAL will be assessed in patients < 18 years of age. Where available, the HAL and pedHAL questionnaire will be distributed to patients to self-complete as specified in the Schedule of Assessments (Table 1).

7.7.1.4 EQ-5D-5L

The EQ-5D-5L is a standardized instrument for use as a measure of QOL outcome (22). It consists of a questionnaire pertaining to 5 dimensions (mobility, self-care, usual activities, pain/discomfort, and anxiety/depression) and a visual analog scale. Scoring of the questionnaire is based on 5 degrees of disability (none, slight, moderate, severe, or extreme). Scoring of the visual analog scale is based on a visual scale ranging from 0 (worst imaginable health state) to 100 (best imaginable health state). Higher scores indicate better health status. The questionnaires will be completed by all patients as specified in the Schedule of Assessments (Table 1).

7.7.2 HJHS

The HJHS is a tool for assessment of joint health in subjects with hemophilia (23). Joint health status will be assessed via the HJHS, as administered by a healthcare professional trained in the use of anthropometric measures, as specified in the Schedule of Assessments (Table 1). Completed HJHS score forms will be collected and archived at study sites.

8 STATISTICS

A Statistical Analysis Plan (SAP) will be finalized before database lock. The plan will detail the implementation of the statistical analyses in accordance with the principal features stated in the protocol.

The primary efficacy and safety analyses will be done for Cohort A and Cohort B separately. A pooled analysis will be performed after all patients have either finished the Month 7 visit during the fitusiran treatment period or discontinued from the study.

8.1 DETERMINATION OF SAMPLE SIZE

Sample size is based on clinical considerations. The overall sample size of 80 patients including approximately 30 patients with inhibitor (Cohort A) and approximately 50 patients without inhibitor (Cohort B) was selected recognizing the limited number of patients with hemophilia, and to yield a reasonably robust estimate of the fitusiran bleeding episode rate and address the secondary objectives, including characterization of safety and tolerability. The proposed sample size is also expected to provide reasonable precision around the ratio of bleeding rate in the fitusiran efficacy period to bleeding rate in the factor or BPA prophylaxis period for both Cohort A and Cohort B.

Since patients will participate in multiple periods, within-patient correlation of numbers of bleeding episodes is expected between the periods. Having no prior knowledge of this correlation, different correlation scenarios were considered and the ratio of the bleeding rate in fitusiran efficacy period to the bleeding rate in factor or BPA prophylaxis period along with its 95% CIs were simulated. For the United States specific requirements see [Section 11.6.1.2](#).

[Table 9](#) and [Table 10](#) summarizes the results from 10,000 simulated studies along with the ABR assumptions.

Table 9 - Simulated ratio of rates for Cohort A, with 95% confidence intervals

| Correlation | Average Ratio (Average 95% CI Bounds), N=30 Based on 10,000 Simulations | |
|-------------|--|--|
| | Fitusiran period ABR: mean=4, SD=6 | |
| | Factor/BPA period ABR: Mean=16; SD=14 | Factor/BPA period ABR: Mean=12; SD=11 |
| 0.25 | 0.24 (0.14, 0.42) | 0.32 (0.19, 0.57) |
| 0.50 | 0.24 (0.15, 0.39) | 0.32 (0.20, 0.52) |
| 0.75 | 0.24 (0.17, 0.35) | 0.32 (0.22, 0.47) |

Abbreviation: ABR=annualized bleeding rate; BPA=bypassing agent; CI=confidence interval; SD=standard deviation

Note: Correlation = within-patient correlation between bleeding episodes of fitusiran efficacy period and factor or BPA period. BPA period ABR per Oldenburg, et al ([24](#)).

Table 10 - Simulated ratio of rates for Cohort B, with 95% confidence intervals

| Correlation | Average Ratio (Average 95% CI Bounds), N=40 Based on 10,000 Simulations | |
|-------------|--|--|
| | Fitusiran period ABR: mean=4, SD=6; N=40 | |
| | Factor/BPA period ABR: Mean=4; SD=5 | Factor/BPA period ABR: Mean=6; SD=7 |
| 0.25 | 1.04 (0.57, 1.94) | 0.69 (0.39, 1.25) |
| 0.50 | 1.03 (0.63, 1.69) | 0.68 (0.43, 1.09) |
| 0.75 | 1.01 (0.72, 1.41) | 0.67 (0.48, 0.93) |

Abbreviation: ABR=annualized bleeding rate; BPA=bypassing agent; CI=confidence interval; SD=standard deviation

Note: Correlation = within-patient correlation between bleeding episodes of fitusiran efficacy period and factor or BPA period. BPA period ABR per Oldenburg, et al (24).

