4.3 NUMBER OF PATIENTS

Approximately 80 patients are planned for enrollment in this study, including approximately 30 patients with inhibitors (Cohort A) and approximately 50 patients without inhibitors (Cohort B). Approximately 18 patients with hemophilia B (including approximately 7 hemophilia B patients in Cohort A, among which are a subgroup of no more than 4 patients who are not responding adequately to BPA prophylaxis [see [Section 5.1](#)]), approximately 11 hemophilia B patients in Cohort B, and approximately 7 adolescents (≥ 12 to < 18 years of age) are also planned for enrollment. For the United States specific requirements, see [Section 11.6.1.2](#).

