8.2.1 Populations to be analyzed

The populations (analysis sets) are defined as follows:

- **Safety Analysis Set:** All patients who enrolled and then received any dose of fitusiran.
- **Efficacy Analysis Set (EAS):** All patients in the safety analysis set who received both factor or BPA prophylaxis and any dose of fitusiran (Addressed in more detail in SAP).
- **Per-protocol Analysis Set (PPS):** All patients in the EAS who had no major protocol deviations. Major deviations will be specified in the SAP.
- **PK Analysis Set:** All patients who received any dose of study fitusiran and have at least 1 postdose blood sample for PK parameters and have evaluable PK data.
- **COVID-19 Unaffected Set:** All patients who had no major or critical protocol deviations due to COVID-19 at any visit up to the end of study (Month 7).
- The subgroup of Cohort A patients who are not responding adequately to BPA prophylaxis treatment will be included in the safety analysis set but will not be part of the efficacy analysis set; however, their efficacy data will be presented separately.

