1.3 DETERMINATION OF SAMPLE SIZE

Sample size is based on clinical considerations. The overall sample size of 80 patients including approximately 30 patients with inhibitor (Cohort A) and approximately 50 patients without inhibitor (Cohort B) was selected recognizing the limited number of patients with hemophilia, and to yield a reasonably robust estimate of the fitusiran bleeding episode rate and address the secondary objectives, including characterization of safety and tolerability. The proposed sample

size is also expected to provide reasonable precision around the ratio of bleeding rate in the fitusiran efficacy period to bleeding rate in the factor/BPA period for both Cohort A and Cohort B.

Since patients participate in multiple periods, within-patient correlation of numbers of bleeding episodes is expected between the periods. Having no prior knowledge of this correlation, different correlation scenarios were considered and the ratio of the bleeding rate in fitusiran efficacy period to the bleeding rate in factor/BPA period along with its 95% CIs were simulated. Below tables summarize the results from 10 000 simulated studies along with the ABR assumptions.

Table 1 - Simulated ratio of rates for Cohort A, with 95% confidence intervals

Correlation	Average Ratio (Average 95% CI Bounds), N=30 Based on 10 000 Simulations	
	Fitusiran period ABR: mean = 4, SD = 6	
	Factor/BPA period ABR: Mean = 16; SD = 14	Factor/BPA period ABR: Mean = 12; SD = 11
0.25	0.24 (0.14, 0.42)	0.32 (0.19, 0.57)
0.50	0.24 (0.15, 0.39)	0.32 (0.20, 0.52)
0.75	0.24 (0.17, 0.35)	0.32 (0.22, 0.47)

Abbreviation: ABR=annualized bleeding rate; BPA=bypassing agent; CI=confidence interval; SD=standard deviation
Note: Correlation = within-patient correlation between bleeding episodes of fitusiran efficacy period and factor or BPA period.

Table 2 - Simulated ratio of rates for Cohort B, with 95% confidence intervals

Correlation	Average Ratio (Average 95% CI Bounds), N=40 Based on 10 000 Simulations	
	Fitusiran period ABR: mean = 4, SD = 6	
	Factor/BPA period ABR: Mean = 4; SD = 5	Factor/BPA period ABR: Mean = 6; SD = 7
0.25	1.04 (0.57, 1.94)	0.69 (0.39, 1.25)
0.50	1.03 (0.63, 1.69)	0.68 (0.43, 1.09)
0.75	1.01 (0.72, 1.41)	0.67 (0.48, 0.93)

[figure not shown]
Abbreviation: ABR=annualized bleeding rate; BPA=bypassing agent; CI=confidence interval; SD=standard deviation

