Note: Correlation = within-patient correlation between bleeding episodes of fitusiran efficacy period and factor or BPA period.

To maintain the previously planned safety database size of at least 244 patients from ATLAS studies, the planned sample size for this study has increased from approximately 70 patients to approximately 80 patients. The detailed rationale for the sample size increase is documented in the position paper in [Appendix F](#).

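### The Cohort B precision table is simulated at N=40 although about 50 patients are planned; Cohort A's N=30 equals enrolment although up to 4 of those patients fall outside the efficacy analysis set

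*Protocol*

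**What the plan says.** Protocol 8.1 gives the planned size: "approximately 30 patients with inhibitor (Cohort A) and approximately 50 patients without inhibitor (Cohort B) was selected". The same section says "The proposed sample size is also expected to provide reasonable precision around the ratio of bleeding rate in the fitusiran efficacy period" to the rate in the prophylaxis period, and claims this for both cohorts. SAP 1.3 repeats the plan and the claim.

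Two simulation tables support the claim, with the same figures in both documents. The Cohort A table (Protocol Table 9, SAP Table 1) is headed "Average Ratio (Average 95% CI Bounds), N=30 Based on 10,000 Simulations" in the protocol. The Cohort B table is headed "Average Ratio (Average 95% CI Bounds), N=40 Based on 10,000 Simulations" in the protocol (Table 10) and "Average Ratio (Average 95% CI Bounds), N=40 Based on 10 000 Simulations" in the SAP (Table 2). Neither section says whether N means enrolled or analysed patients.

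SAP 1.3 explains the rise from about 70 to about 80 patients: "To maintain the previously planned safety database size of at least 244 patients from ATLAS studies". For the detailed rationale it points to a position paper in Appendix F.

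Protocol 4.3 counts within Cohort A "a subgroup of no more than 4 patients who are not responding adequately to BPA prophylaxis". These patients skip the BPA prophylaxis period, and Protocol 8.2.1 says that they "will be included in the safety analysis set but will not be part of the efficacy analysis set". SAP 2.3 agrees. The primary ratio is analysed on the efficacy analysis set, separately by cohort. In the current SAP that set is EAS 1, the patients dosed before dose resumption (SAP 2.3 and 2.4.4).

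**The concern.** The study has no power target, so the precision statement is the only statistical argument offered for its size. The argument should describe the patients who are planned to be analysed, and in neither cohort does it clearly do so.

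In Cohort B the text says about 50 and the table says 40, within one section of each document. In Cohort A the table uses the enrolment figure, although a defined part of that enrolment has no on-study BPA period and cannot contribute to a within-patient ratio. The two mismatches point in opposite directions: the Cohort B intervals are too wide for the plan, and the Cohort A intervals are too narrow if the direct-entry places are filled.

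What is at stake is a correct record of planned precision. Someone who sets the achieved intervals beside these tables would be using the wrong N.

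**Working it through.** **Inputs.** All come from Protocol 8.1 and SAP 1.3 unless marked.
- Planned enrolment: A about 30, B about 50. Tabulated N: A 30, B 40.
- Fitusiran-period ABR: mean 4, SD 6. Prophylaxis-period ABR: A 16 (SD 14) or 12 (SD 11); B 4 (SD 5) or 6 (SD 7).
- Within-patient correlation ρ: 0.25, 0.50, 0.75.
- Direct-entry patients outside the efficacy set: at most 4 (Protocol 4.3 and 8.2.1), so A may be 30 − 4 = 26 before withdrawals. The documents give no withdrawal rate and none is assumed here.

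**Step 1: can the published intervals be reproduced?** For a paired ratio with equal follow-up, approximately

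SE(log ratio) = √[(CV₁² + CV₂² − 2ρ·CV₁·CV₂)/N], with CV = SD/mean.

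- Cohort A, ABR 16, ρ = 0.25: CV₁ = 6/4 = 1.5 and CV₂ = 14/16 = 0.875. The bracket before division by N is 2.25 + 0.766 − 0.656 = 2.359. At N=30 the SE is 0.280. The published interval gives ln(0.42/0.14)/(2 × 1.96) = 0.280. Over the six Cohort A cells the published widths imply N between 27.4 and 30.8, in line with 30.
- Cohort B, ABR 6, ρ = 0.50: CV₂ = 7/6 = 1.167. The bracket is 2.25 + 1.361 − 1.75 = 1.861. At N=40 the SE is 0.216. The published interval gives ln(1.09/0.43)/(2 × 1.96) = 0.237, which implies N of about 33. Over the six Cohort B cells the implied N is 29.4 to 34.6.

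Simulation gave the same pattern (4,000 trials per cell, correlated negative binomial counts, sandwich SE). Cohort A matched at N=30 to within about 0.01 when 162-day Poisson variation was added and bounds were averaged on the log scale. Cohort B did not match at N=40: the widest variant gave 1.04 (0.61 to 1.81) against the published 1.04 (0.57 to 1.94). With 162-day Poisson variation the published Cohort B widths imply N of 34 to 40. No variant implies 50. The Cohort B table therefore cannot be read as a run at 50 with a wrong label.

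**Step 2: rescale the published intervals.** Because the simulation settings are not given, I keep the published widths and change only N:

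new bound = ratio × (bound/ratio)^√(N_table/N_new)

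- B, 40 to 50: √(40/50) = 0.894, so log widths narrow by about 11% (equivalently, the published ones are 1/0.894 = 1.118, about 12% too wide for 50).
- A, 30 to 26: √(30/26) = 1.074, so log widths grow by about 7%. At 28 the factor is √(30/28) = 1.035; at 30 nothing changes.

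| Cohort, prophylaxis ABR | ρ | Published | Rescaled |
|---|---|---|---|
| B, 4 (N=50) | 0.25 | 1.04 (0.57, 1.94) | (0.61, 1.82) |
| | 0.50 | 1.03 (0.63, 1.69) | (0.66, 1.60) |
| | 0.75 | 1.01 (0.72, 1.41) | (0.75, 1.36) |
| B, 6 (N=50) | 0.25 | 0.69 (0.39, 1.25) | (0.41, 1.17) |
| | 0.50 | 0.68 (0.43, 1.09) | (0.45, 1.04) |
| | 0.75 | 0.67 (0.48, 0.93) | (0.50, 0.90) |
| A, 16 (N=26) | 0.25 | 0.24 (0.14, 0.42) | (0.13, 0.44) |
| | 0.50 | 0.24 (0.15, 0.39) | (0.15, 0.40) |
| | 0.75 | 0.24 (0.17, 0.35) | (0.17, 0.36) |
| A, 12 (N=26) | 0.25 | 0.32 (0.19, 0.57) | (0.18, 0.59) |
| | 0.50 | 0.32 (0.20, 0.52) | (0.19, 0.54) |
| | 0.75 | 0.32 (0.22, 0.47) | (0.21, 0.48) |

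In all 12 rows the interval includes or excludes 1 exactly as published.

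**The case against.** The strongest reply is that nothing turns on this. The size rests on clinical considerations, and SAP 1.5 says the study is not powered to detect a difference. If precision at 40 is reasonable, precision at 50 is better. Each table prints its N, so a careful reader is not deceived. The Amendment 05 history (Protocol 11.7.5) records 79 patients already enrolled when the target became 80, so a new simulation could not have guided recruitment. Appendix F of the SAP might also deal with precision at the larger size. On Cohort A, about 30 is loose, 4 is a ceiling that may not be reached, and N is undefined.

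Most of this stands and sets the severity. It does not remove the mismatch: both sections make the precision claim for about 50 patients and print intervals for 40, without a word in the section itself to connect them. Appendix F could not be checked, so I do not say that the sponsor overlooked precision at 50, only that SAP 1.3 as printed does not address it.

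Three stronger readings are tempting and are not supported.
- A reader might infer that at 50 the row with prophylaxis ABR 6 and ρ = 0.50 would exclude 1. Rescaling leaves its upper bound at about 1.04. Models that give a narrower interval also fail to reproduce the published table at N=40, so they cannot settle the matter.
- A reader might infer from that failure that the Cohort B table is miscalculated. The count distribution, follow-up, dropout and averaging rule of the simulation are not documented, so a mismatch with my models does not show an error.
- A reader might take Cohort A precision to be overstated as a fact. It is overstated only if direct-entry places are filled within an enrolment of about 30.

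**Conclusion.** The point holds at low severity. The Cohort B mismatch, about 50 in the text against 40 in the table, is certain from the printed labels and is conservative: the log-scale intervals narrow by about 11% at 50. The Cohort A point is secondary and conditional: about 7% wider if all 4 direct-entry places are filled, less if fewer are, with the highest upper bound about 0.59.

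The sizes assume that interval width scales with 1/√N and that every planned patient outside the direct-entry subgroup enters the primary analysis. Exact bounds need the sponsor's own simulation program. EAS 1 leaves out any patient dosed only after resumption, and SAP 2.4 reports only 2 participants on the later regimen, so about 50 is an upper figure for Cohort B. The documents give no ground for concluding that the study is too small or that its analysis should change.

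**What to change.** Re-run the same simulation, or rescale the published intervals and say so. Define N as the patients expected in the set used for the primary ratio: EAS 1 in the current SAP, at most about 50 in Cohort B and about 26 to 30 in Cohort A. Replace SAP Tables 1 and 2 and add one sentence saying what N means. Update Protocol Tables 9 and 10 only if the protocol is amended again; this does not justify a separate submission.

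The cost is one simulation run or a short calculation, two SAP tables and one sentence. Recruitment and analysis do not change, and no extra patients are needed. The one downside is a slightly less favourable stated precision for Cohort A.
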